1.5 Risks and Benefits for Subjects

To date, no clinical studies of OP0201 have been conducted in humans. Thus, information regarding expected risks and benefits is unknown.

The clinical safety and tolerability of OP0201 (DPPC:CP 20:1 w/w) for human use is guided by the limited data from human exposure to other formulations (see Section 1.1.2) and animal studies. Of the 9 subjects exposed to study drug containing DPPC and CP, no SAEs or deaths were reported. Safety and proof-of-concept results from animal pharmacology studies are considered supportive of the formulation intended for humans. Across several nonclinical pharmacology studies, the beneficial effects of a formulation of DPPC:CP 200:1 w/w were consistently better than those of no treatment and treatment with propellant alone (ie, placebo).¹⁵ No AEs were observed in any of the animal studies.

DPPC and CP are listed as ingredients in other marketed products indicated for the prevention of RDS in premature neonates. The safety and tolerability of these products is summarised in the IB.

Propellant HFA-134a is used in marketed nasal products and is also present in OP0201. HFA-134a has a good safety and tolerability profile in patients suffering from perennial allergic rhinitis.²²

The most frequent AEs for 578 placebo-treated (HFA-134a) adults and adolescents with seasonal or perennial allergic rhinitis from short term (2-6 wk) controlled trials were: nasal discomfort (4.8%), epistaxis (1.2%), and headache (1.6%).²³ Nasal ulcerations occurred in 2 subjects treated with placebo in these studies. The most frequent AEs for 111 placebo-treated (HFA-134a) adults and adolescents with perennial allergic rhinitis from a long-term (52 wk) controlled trial were: epistaxis (2%; 2/111; 1 mild, 1 moderate intensity). A total of 3 subjects treated with placebo withdrew from the study due to an adverse reaction. No erosions or ulcerations were noted in subjects who received placebo in this study. No subject experienced a nasal septum perforation during the trial.

2 STUDY OBJECTIVES

2.1 Primary Objective

The primary objective of this study is:

• To assess the safety of intranasal OP0201 20 mg compared to placebo

2.2 Exploratory Objectives

The exploratory objectives of this study are:

- To assess the effect of intranasal OP0201 20 mg compared to placebo on ear pain scores using the Visual Analog Scale (VAS)
- To assess the effect of intranasal OP0201 20 mg compared to placebo on ear pain scores using the Numeric Rating Scale (NRS-11)
- To assess impression of global change in symptoms as measured by Patient Global Impression of Change (PGIC)
- To assess impression of global change in symptoms as measured by the Clinical Global Impressions Scale: Global Improvement (CGI-I)
- To assess the effect of intranasal OP0201 20 mg compared to placebo on AOM symptoms
- To assess the blinding efforts as measured by the Blinding Index (BI)
- To evaluate subject experience with the device as measured by the Device Experience Questionnaire-Subject
- To evaluate study staff experience with the device as measured by the Device Experience Questionnaire-Study Staff Administering the Treatment

3 INVESTIGATIONAL PLAN

3.1 Overall Study Design and Plan

This will be a single-dose, double-blind, placebo-controlled, randomised, parallel-group, proof-of-concept study to evaluate the safety and immediate (within 60 min) reduction of ear pain caused by AOM in adults following a single dose of intranasal OP0201 20 mg or placebo.

All study-related procedures, including screening, will be performed on Day 1. Following Screening, but before any treatment-related procedures, eligible subjects will be randomly assigned to 1 of the following groups:

- Single intranasal dose of OP0201 20 mg (4 sprays per nostril for a total of 8 sprays)
- Single intranasal dose of placebo (4 sprays per nostril for a total of 8 sprays)

Ear pain will be assessed in the left and the right ear separately, at predose and at 10, 20, 30, and 60 min post dose using the VAS and the NRS-11. Global impression of change in symptoms will be rated by the subject at 10, 20, 30, and 60 min post dose using the PGIC. The physician investigator will rate global impression of change at 60 min post dose using the CGI-I. AOM symptoms (tinnitus, dizziness, vertigo, and feeling of fullness or muffled hearing in the ear) will also be evaluated at predose and at 60 min post dose.

Safety evaluations include vital signs measurements, ENT examination using otoscopy, appearance of the TM, and AEs. Vital signs (oral temperature, respiratory rate, pulse, and blood

pressure) will be measured (after 3 min of rest in the supine position) predose and at 60 min post dose. An ENT examination (otoscopy of the ear, nose, and oropharynx) will be performed by the physician investigator (physician qualified to perform an otoscopic exam of the ears, nose, and oropharynx) at predose and at 60 min post dose. All spontaneously reported AEs will be recorded. The appearance of the TM (contour, color, fluid, and translucency) will also be evaluated using otoscopy by the physician investigator at predose and at 60 min post dose. The appearance of the TM will be evaluated in both ears separately, regardless if AOM is bilateral or unilateral.

After the subject has completed all assessments on Day 1, the BI will be administered separately to the subject and physician investigator prior to the subject leaving the study centre. The Device Experience Questionnaire will be administered to the subject following the BI before the subject leaves the centre.

Any study staff who administer treatment to subjects will also complete the Device Experience Questionnaire. Any study staff who administered treatment only needs to complete the questionnaire one time for the study, not for each subject treated.

Subjects will receive a follow-up safety call 1 wk after treatment, and reported AEs and concomitant medications will be recorded.

3.2 Study Duration

Duration of treatment, including Screening, will be 1 d. Subjects will receive a follow-up safety call 1 wk after study drug administration and exit the study.

3.3 Selection of Study Population

The study population consists of adult subjects with a confirmed diagnosis of AOM. Specific entry criteria are detailed in Section 3.3.1 and Section 3.3.2.

3.3.1 Inclusion Criteria

Subjects must satisfy all of the following criteria to be included in the study:

- 1. Male and female subjects must be ≥ 18 y of age.
- 2. Subjects must have confirmed AOM diagnosis with moderate to severe bulging of the TM and recent (< 48 hours [h]) onset of ear pain.
- 3. Have moderate to severe ear pain in the affected ear(s), defined as a score of \geq 5 (on a scale of 0-10) on the NRS-11 as evaluated by the subject at Screening.
- 4. Generally good health (other than AOM) as determined by evaluation of medical history and physical examination at Screening.
- 5. Negative urine pregnancy test at Screening for all female subjects of childbearing potential. Results must be available prior to randomisation.
- 6. Able to read and sign written informed consent prior to study participation.

3.3.2 Exclusion Criteria

Subjects who meet any of the following criteria will be disqualified from entering the study:

- 1. Presence of a perforated TM at Screening (must be able to rule out perforated TM by speculum examination, impedance testing tympanometry, otoscopy, or Valsalva maneuver), or had a perforated TM within 6 months (mo) prior to Screening as determined by medical history
- 2. Subjects with tympanostomy tubes
- 3. Acute or chronic otitis externa
- 4. Chronic OM defined as confirmed presence of MEE for 12 wk or longer
- 5. Disorders with decreased mucociliary clearance or higher viscosity of the mucous (eg, cystic fibrosis, primary ciliary dyskinesia, Kartagener's syndrome)
- 6. Clinically relevant blockage of 1 or both nasal passages, as determined by the investigator's medical judgment
- 7. Permanent hearing loss irrespective of OM
- 8. Subjects with medical conditions that may affect interpretation of the safety or efficacy of study drug as determined by the investigator's medical judgment
- 9. Subjects with craniofacial abnormalities (eg, cleft palate, Down's Syndrome)
- 10. Subjects with erythema of the TM without other evidence of OM
- 11. Seborrheic dermatitis involving the affected external ear canal or pinna
- 12. Use of medications with known vasoconstrictive properties (eg, decongestants [Afrin[®], Sudafed[®]]) currently or within 2 h prior to Screening
- 13. Use of oral analgesics < 2 h prior to Screening or Baseline (oral analgesics > 2 h are permitted as long as ear pain criteria are met per Inclusion Criteria)
- 14. Known hypersensitivity to DPPC, CP, or HFA-134a
- 15. Female subjects who are pregnant or lactating
- 16. Clinically significant mental illness that may interfere with the conduct of the study (as determined by the investigator at Screening)
- 17. Exposure to any study drug within 30 d prior to Screening.
- 18. Investigator and study centre personnel directly affiliated with this study and/or their immediate families (defined as spouse, significant other, parent, child, or sibling, whether adopted or biologic)
- 19. Subject has a condition or is in a situation that, in the investigator's opinion, may put the subject at risk, may confound the study results, or may interfere significantly with the subject's participation in the study

3.3.3 Removal of Subjects from Therapy or Assessment

A subject will be considered to have completed the study when he or she completes the follow-up safety call on Day 7. If a subject is discontinued at any time after randomisation into the study, but before 60 min post dose, the investigator will make every effort to follow the

subject and complete the assessments at 60 min post dose/early termination assessments as shown in Section 3.5.1. Subjects who discontinue the study prematurely will be replaced.

A termination electronic case report form (eCRF) page should be completed for every subject who receives study drug, whether or not the subject completes the study. The reason for any early discontinuation should be indicated on this form. The primary reason for a subject discontinuing early should be selected from the following standard categories of early termination:

- *Adverse Event (Adverse Reaction)*: Clinical events occurred that, in the medical judgment of the investigator for the best interest of the subject, are grounds for discontinuation. This includes serious and nonserious AEs regardless of relation to the study drug.
- *Death:* The subject died.
- *Withdrawal of Consent*: The subject desired to withdraw from further participation in the study in the absence of an investigator-determined medical need to withdraw. If the subject gave a reason for withdrawing, it should be recorded in the eCRF.
- *Protocol Violation*: The subject's findings or conduct failed to meet the protocol entry criteria or failed to adhere to the protocol requirements (eg, drug noncompliance, failure to complete all assessments). The violation necessitated early discontinuation from the study.
- *Lost to Follow-Up*: The subject did not complete the follow-up safety call and study personnel were unable to contact the subject.
- *Other*: The subject was discontinued for a reason other than those listed above, such as theft or termination of study by sponsor.

3.4 Treatments

3.4.1 Details of Study Treatments

OP0201 is a drug-device combination product that comprises a novel formulation of 2 active ingredients (DPPC and CP) suspended in propellant (HFA-134a), an inactive ingredient. There are no other ingredients (ie, no excipients, no fillers) in the formulation. The drug product is formulated as a dry powder suspended in propellant and delivered via a metered-dose inhaler (MDI). The active ingredients are synthetically derived and none of the ingredients contain animal or human derivatives.

The OP0201 MDI container should be stored at room temperature between 68°F and 77°F (20°C and 25°C, respectively); excursions are permitted from 59°F and 86°F (15°C and 30°C, respectively). Store the MDI container with the actuator down.

The sponsor will provide all study drug materials.

Information about the study drugs is provided in Table 3.1.

Table 3.1: Details of Study Drugs

	Active	Placebo	
Name	OP0201	Not applicable	
Dose	20 mg (4 sprays per nostril; each 0.1 mL spray is 2.5 mg OP0201). Total of 8 sprays = 1 dose.	0 mg (4 sprays per nostril; each 0.1 mL spray is 0 mg OP0201). Total of 8 sprays = 1 dose.	
Route	Intranasal	Intranasal	
Formulation	Metered dose inhaler	Metered dose inhaler	
Strength	20 mg	0 mg	

Abbreviations: USA = United States of America

3.4.2 Dosage Schedule

Subjects will receive a single intranasal dose (4 sprays per nostril for a total of 8 sprays) of OP0201 20 mg or placebo.

3.4.3 Treatment Assignment

Following Screening, but before any treatment-related procedures, eligible subjects will be randomly assigned in a 1:1 ratio to 1 of the following groups:

- Single intranasal dose of OP0201 20 mg (4 sprays per nostril for a total of 8 sprays)
- Single intranasal dose of placebo (4 sprays per nostril for a total of 8 sprays)

3.4.4 Drug Packaging and Blinding

OP0201 and placebo will be packaged and labeled by Catalent in accordance with applicable national laws.

Kits containing OP0201 or placebo will be identical in appearance and will be provided to the study sites. Kit numbers for OP0201 and placebo will be randomly assigned through the Interactive Response Technology system using a randomisation list.

All subjects and clinical staff will be blinded to the assigned treatment. The PI will be ultimately responsible for ensuring that the integrity of the blind is maintained throughout the study, and will be required to notify the sponsor in the event of any breaking of the blind for any reason.

If an SAE occurs during the study that meets the criteria for expedited reporting (ie, is a Suspected Unexpected Serious Adverse Reaction), the subject will be unblinded by WCT pharmacovigilance. In an emergency situation, the investigator may unblind the study subject's treatment assignment. When possible, the Medical Monitor should be notified prior to

unblinding. The investigator should inform the Medical Monitor of the unblinding if there is no notification prior to the unblinding.

3.4.5 Drug Inventory and Accountability

The investigator must keep an accurate accounting of the number of study drug units delivered to the site, dispensed to subjects, and returned to the sponsor at the completion of the study. The study drug must be dispensed for subjects by an appropriately qualified study staff member who will be administering the treatment to the subject. The study drug is to be used in accordance with the protocol by subjects who are under the direct supervision of the investigator. Investigators should maintain records that document adequately that the subjects were provided the doses specified by the protocol and reconcile all study drugs, including unused, partially used, and empty containers, as well as devices, will be returned to the sponsor sorted as per subject.

3.4.6 Treatment Compliance

Administration of study drug will be performed by study personnel to ensure accuracy of study drug delivery and compliance.

3.4.7 Prior and Concomitant Illnesses and Treatments

3.4.7.1 Prior and Concomitant Illnesses

Investigators should document all significant illnesses that the subject has experienced within 6 mo of Screening. Additional illnesses present at the time informed consent is given are to be regarded as concomitant illnesses. Illnesses first occurring or detected during the study and/or worsening of a concomitant illness during the study are to be documented as AEs on the eCRF.

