3.5.5 Safety Assessments

Ear, Nose, and Throat Examination: Examination of the ear, nose, and oropharynx will be performed using otoscopy at Screening and at 60 min post dose.

Otoscopy: Otoscopy assessments will be performed by the physician investigator to assess the appearance of the TM in the left and right ear. Measurements will be taken at Baseline and at 60 min post dose. The TM will be rated for the following variables:

- Contour: normal, retracted, full, bulging, or perforated
- Color: normal, partly red, or completely red
- Fluid behind the TM: no/yes; if yes-yellow, translucent, red, blue, or black
- Translucency: translucent, semi-opaque, or opaque

Details of how each variable is to be assessed and categorised are provided in Appendix 8.2.

Vital Signs: Vital signs will be measured at Baseline and at 60 min post dose or Early Termination. Vital signs will include oral temperature (C), respiratory rate (breaths per minute), pulse (beats per minute [bpm]), and systolic and diastolic blood pressure (BP) recorded after at least 3 min of rest in the supine position. Body weight (kg) will also be collected with the vital signs measurements at Baseline only. Repeat measurements may be obtained in the event the initial measurements taken at Baseline are out of range.

Adverse Events: All AEs occurring after the administration of study treatment until the follow-up safety call or early termination will be recorded.

See Section 4, for additional information.

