4 ADVERSE EVENT REPORTING

Throughout the course of the study, all AEs will be monitored and recorded on an AE eCRF, including the AE's description, start and end date, seriousness, severity, action taken, and relationship to the study drug. If AEs occur, the first concern will be the safety of the subjects. All AEs will be followed until resolved or stable and the outcome documented on the eCRF.

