4.2 Reporting Procedures and Requirements

4.2.1 Adverse Events

AE recording will begin at administration of study drug. Any AEs occurring before the start of treatment (ie, before administration of study drug) will be recorded in the medical history. Also, the sign, symptom, or disease present before starting the treatment period are only considered AEs if they worsen after starting the treatment period.

If the investigator detects an AE in a study subject after the follow-up safety call and considers the event possibly related or related to prior study treatment, the investigator should report it to the WCT.

The investigator should report all AEs on the AE page(s) of the eCRF and source documents, regardless of seriousness, severity, and causality. Whenever possible, an AE will be reported using a diagnostic term, (eg, "common cold" or "upper respiratory infection" rather than "runny nose, cough, mild fever") and should be described with the attributes described in Section 4.1.4.

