11. SAFETY PARAMETERS

Safety parameters will be listed for the Randomized Population and summarized for the Safety Population unless otherwise noted.

11.1 **AEs**

AEs reported from time of first dose through EOS will be coded according to MedDRA® version 21.1 or later. Each reported AE will be mapped to a PT and SOC. Aside from parameters collected on the eCRF, listings will include date and time of study treatment dosing, MedDRA PT and SOC, Study Day, whether or not the AE is ongoing, AE duration, and whether or not the AE resulted in study discontinuation. For AEs that are ongoing, AE end date will be imputed with subject-level EOS date for the duration calculation.

A treatment-emergent AE (TEAE) will be defined as an AE that began or worsened during or after study treatment dosing on Day 1 and no later than on Day 2. AEs with insufficient date or time information to determine whether or not they were treatment-emergent will be considered treatment-emergent. AEs that began or worsened in severity from Day 3 through EOS will be defined as non-treatment-emergent. AEs that began or worsened in severity before first dose will be recorded as medical history.

All TEAEs will be listed. In addition, separate listings will be done for:

- Treatment-emergent SAEs (TESAEs), to include seriousness criteria
- TEAEs that resulted in study treatment interruption or dose reduction

Confidential Page 16 of 33

- TEAEs that results in discontinuation from the study or study treatment (excluding deaths)
- TEAEs that resulted in death
- Non-treatment-emergent AEs

Listings will be done for the Safety Population.

Incidence of all TEAEs will be summarized by SOC and PTs within SOCs, sorted alphabetically by SOC and PT within SOC unless otherwise noted. In addition, separate summaries will be done for:

- TEAEs assessed as related to study treatment
- TEAEs by maximum severity, with both SOCs and PTs within SOCs sorted by descending incidence among all Study Participants combined
- TESAEs
- TESAEs assessed as related to study treatment

In summaries by relationship to study treatment and maximum severity, missing relationship will be considered related and missing severity will be considered severe. Only the most related TEAE per subject for a given PT will be counted in summaries by relationship; similarly, only the most severe TEAE will be counted in summaries by severity.

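### Protocol 3.4.7.1 conflicts with the rule that adverse events start at dosing, and a pre-dose event entered under it with only a Day 1 date would count as treatment-emergent (minor)

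*Protocol*

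**What the plan says.** Protocol 3.4.7.1 gives sites two instructions. The first is that "Additional illnesses present at the time informed consent is given are to be regarded as concomitant illnesses". The second is that "Illnesses first occurring or detected during the study and/or worsening of a concomitant illness during the study are to be documented as AEs". The second is not tied to dosing.

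The rest of the plan is. Protocol 3.5.5 states that "All AEs occurring after the administration of study treatment until the follow-up safety call or early termination will be recorded". Protocol 4.2.1 states that "AE recording will begin at administration of study drug" and that "Any AEs occurring before the start of treatment (ie, before administration of study drug) will be recorded in the medical history". It adds that signs, symptoms or diseases already present "are only considered AEs if they worsen after starting the treatment period". The screening and baseline procedures in Protocol 3.5.2.1 include no AE collection, and the AE row of the assessment schedule (Protocol Table 3.2, repeated in SAP Appendix A) has no screening/baseline mark. SAP 11.1 assigns events that began or worsened before the first dose to medical history. SAP 9.7 does the same for abnormal physical examination findings.

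Three provisions on timing also matter. Protocol 3.1 puts screening and dosing on the same day. Protocol Section 4 lists, among the items recorded for each AE, "start and end date, seriousness, severity, action taken, and relationship to the study drug". SAP 11.1 counts as treatment-emergent any "AEs with insufficient date or time information to determine whether or not they were treatment-emergent".

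**The concern.** Sites decide which eCRF page an illness goes on, and the protocol gives them two incompatible rules for the interval between consent and dosing. A site that follows 3.4.7.1 puts a pre-dose illness on the AE page; a site that follows 4.2.1 puts it in medical history. Detection is a second trigger. A condition that was there all along but is first noticed at the repeat ENT examination or otoscopy at 60 minutes is an AE under 3.4.7.1, and is not one under 4.2.1 unless it worsened.

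AE incidence is the first primary endpoint in SAP 4.2.1. If pre-dose illness reaches the treatment-emergent tables, incidence in a small trial rises for reasons unrelated to treatment, and the comparison between arms becomes noisier.

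**Working it through.** The plan states no figure on this point, so the check sets the rules side by side and then sizes one misclassified subject.

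**Step 1. Where the rules disagree**

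| Illness | Protocol 3.4.7.1 | Protocol 4.2.1 and SAP 11.1 | Conflict |
|---|---|---|---|
| Present and known at consent, no worsening | Concomitant illness | Not an AE | No |
| Arises between consent and dosing | AE | Medical history | Yes |
| Concomitant illness that worsens between consent and dosing | AE | Medical history | Yes |
| Present before dosing, first detected later, no worsening | AE by detection; also a concomitant illness if present at consent | Not an AE | Yes |
| Arises or worsens after dosing | AE | AE | No |

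The fourth row also shows 3.4.7.1 at odds with itself: an illness present at consent but found afterwards meets both of its instructions.

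**Step 2. Whether the conflict reaches the analysis**

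- Protocol 4.1.1 and SAP 11.1 both require onset or worsening at or after dosing. If onset is known to be before dosing, the event is not treatment-emergent, whichever page it is on.
- SAP 8.6 defines Study Day 1 as the day of dosing. An event dated Day 1 cannot be placed before or after the dose by its date. A clock time or a flag is needed.
- Protocol Section 4 names start and end dates and no time.
- If the time is not captured, the SAP 11.1 default makes the event treatment-emergent. SAP 8.5 points the same way for missing dates.

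So two things must both happen: the site enters the illness as an AE under 3.4.7.1, and its onset relative to dosing is not recorded.

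**Step 3. Size**

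Inputs: 12 subjects per arm and 24 in total (Protocol 5.2.1). One misclassified subject with no other treatment-emergent event adds

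- in that arm: 1/12 = 8.3 percentage points;
- overall: 1/24 = 4.2 percentage points.

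The documents give no misclassification rate. For an assumed per-subject rate p, the expected number is 24p and the chance of at least one is 1 − (1 − p)^24:

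| Assumed p | Expected of 24 | Chance of at least one |
|---|---|---|
| 2% | 0.5 | 38% |
| 5% | 1.2 | 71% |
| 10% | 2.4 | 92% |

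These rates are illustrative. The interval at issue is part of one day, so the lower end is the more plausible.

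**Step 4. Direction**

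An event that precedes dosing cannot be caused by the treatment, and allocation is randomised and blinded, so the expected rate p is the same in both arms. If p is independent of genuine events and the true incidence in an arm is π, the observed incidence is π + (1 − π)p. The difference between arms becomes (1 − p) times the true difference: it shrinks by 2% to 10% of its own size over the assumed range, and its sign is unchanged. What remains is raised incidence in both arms and chance imbalance.

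**The case against.** The strongest reply is that this is loose wording in one sentence of a section about illness history, and that the operative sections agree with each other. Several parts of that reply stand.

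- A reader might infer that any illness found at screening becomes an AE. The documents do not support this. 3.4.7.1 itself treats illness present at consent as concomitant, most illness found at a same-day screening examination will have been present at consent, and SAP 9.7 sends abnormal physical examination findings to medical history.
- A reader might infer that the shared Day 1 alone turns pre-dose illness into treatment-emergent events. It does not. Both definitions exclude known pre-dose onset, and the default applies only when timing is insufficient.
- The AE page of the eCRF is not among the documents. The list in Protocol Section 4 is introduced as non-exhaustive, SAP 11.1 speaks of time as well as date, and SAP 8.6 defines duration in minutes as well as days. Onset time may well be collected. Protocol 5.1 also provides for queries on omissions.
- A reader might set 8.3 points against the 4.8% nasal discomfort rate quoted in Protocol 1.5. That is not like for like: the 4.8% is one event type over 2 to 6 weeks of propellant use, and the 8.3 points is any-event incidence after a single dose. SAP 11.1 also tabulates events by preferred term and relatedness, so an unrelated illness would not mask a nasal signal.

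The contradiction itself survives. Protocol 5.2 gives the SAP precedence over analyses described in the protocol; it does not tell a site which page to use. No provision in the documents says that 4.2.1 overrides 3.4.7.1.

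**Conclusion.** Protocol 3.4.7.1 is wrong as written, and the point is minor. It contradicts Protocol 3.5.5 and 4.2.1 and SAP 11.1 for illness arising or worsening between consent and dosing, and for pre-existing illness first detected later without worsening. The route to the primary endpoint is conditional on both steps identified above, and the documents do not settle whether onset time is captured. Each affected subject with no other treatment-emergent event is worth 8.3 points in an arm. How many there would be is unknown and probably few.

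A claim that the trial's safety comparison is biased would go too far. Given randomised, blinded dosing, the expected consequence falls on both arms alike.

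**What to change.** Reword Protocol 3.4.7.1 so that an illness is an AE only if its onset follows study drug administration, or if it was pre-existing and worsens after administration. State that every other illness, including one merely first detected later, is recorded as medical history, in line with 4.2.1. Moving the cut-off to dosing while keeping detection as a trigger would not be enough: a pre-existing, unworsened condition first seen at 60 minutes would still become an AE, contrary to 4.2.1.

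Confirm that the AE page records onset time, or a before/after-dose flag, for events dated Day 1. Add one if it does not. The SAP 11.1 default can stay as it is, because it will then reach only events whose timing is truly unknown.

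The cost is one wording change and, if the field is missing, one extra entry for each Day 1 event.
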